Bleeding Assessment		X	X	X	X	X	X	X	X	X	X	X	X
Concomitant Therapy	X	X	X	X	X	X	X	X	X	X	X	X	X
Reporting of Outcome Events			In an expedited fashion – reporting timelines the same as for SAEs										
Adverse Events	X	X	X	X	X	X	X	X	X	X	X	X	X
Termination of Trial Medication											X ¹⁹		
End of Patient Participation												X ²⁰	X ²⁰

Proprietary confidential information.

© 2016 Boehringer Ingelheim International GmbH or one or more of its affiliated companies. All rights reserved.

This document may not - in full or in part - be passed on, reproduced, published or otherwise used without prior written permission.

¹ Screening and randomisation will occur after successful PCI.

² End of treatment (EOT) procedures to be completed by all patients at the time of study drug discontinuation. For patients who discontinue early, the EOT visit should be performed instead of the scheduled trial visit at time of discontinuation.

³ For patients that complete all scheduled visits or discontinue treatment early, follow up visit to be conducted four weeks after EOT.

⁴ For patients that discontinue treatment early, the final visit will take place at the time trial conclusion is declared.

⁵ To be conducted by telephone.

⁶ This event driven trial is expected to take place over 30 months, however, the trial can conclude earlier if an adequate number of events is reported sooner. It can conclude later (or enrol additional patients) if more time is needed to observe the minimum number of required events. If it continues beyond 30 months, follow-up visits (with same assessments as required at visits 9 and 11) will occur every 6 months with telephone visits (with the same assessments as required at visits 10 and 12) in between. At the time of trial conclusion (when adequate number of events were reported), all patients would be notified of study conclusion and have an EOT and follow up visit (patients that complete all scheduled visits) or final visit (premature treatment discontinuation) scheduled. Patients who discontinue study treatment early should continue to attend regularly scheduled visits. Refer to [Section 6.2.2](#) for details on management of patients that wish to reduce study participation for any reason. Collection of vital status and endpoints for all patients at the end of the trial is important and described in [Section 6.2.3](#).

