All OEs will be adjudicated by blinded adjudication experts. Blinding of all event documentation will be performed by trained specialists. The role of the IAC will be to oversee and perform the blinded adjudication of all outcome events. This Committee will report to the Executive Steering Committee and DMC.

3. Bleeding Questionnaire:

Proprietary confidential information.

© 2016 Boehringer Ingelheim International GmbH or one or more of its affiliated companies. All rights reserved.

This document may not - in full or in part - be passed on, reproduced, published or otherwise used without prior written permission.

A questionnaire querying patients for signs and symptoms of bleeding will be administered at each visit. The goal is to reduce the possibility of under-reporting of events. All symptoms will be evaluated and if potentially consistent with an outcome event will be referred to the IAC.

4. Review of Data for Clinical Events:

Any AE that indicates potential loss of neurological function, such as unilateral weakness, loss of vision or sensory disturbance will trigger a request for more information from the centre for event adjudication if potentially consistent with an outcome event. Any decrease in haemoglobin of >2g/dL will be similarly investigated.

5. Data Handling:

Patients will be randomly allocated to the treatment arms via IRT. Wherever feasible, data management will be undertaken without knowledge of patient treatment allocation. Special procedures to handle data with the potential for unblinding, such as INRs, will be specified. By treatment data tabulations will not be reviewed during the course of the trial and the data management personnel will not have access to the randomisation code.

By implementing these appropriate measures to avoid bias, the PROBE design is an acceptable [[R14-0530](#)] and preferred approach for this study.

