5.2.2 Assessment of adverse events

5.2.2.1 Assessment of Bleeding events

Patients should be carefully assessed for signs and symptoms of bleeding. Bleeding will be classified as major, Clinically Relevant Non Major Bleeding Event (CRNMBE) or minor. Major bleeds will be further sub classified as life-threatening and other major bleeds. The location of the bleeding including the specific critical area or organ into which the bleeding occurred and whether or not it prolongs hospitalisation will be recorded. The following definitions are specified for bleeds:

Definition of a major bleed

Major bleeds will be defined according to the ISTH definition of a major bleed, as follows [[R05-0344](#)].

- Symptomatic bleeding in a critical area or organ, such as intracranial, intraspinal, intraocular, retroperitoneal, intra-articular or pericardial, or intramuscular with compartment syndrome

and/or

- Bleeding associated with a reduction in haemoglobin of at least 2g/dL (1.24mmol/L), or leading to transfusion of two or more units of blood or packed cells¹

and/or

- Fatal bleed

Definition of a CRNMBE

A clinically relevant non-major bleeding event is a clinically overt bleed that does not meet

¹ Bleeding should be overt and the haemoglobin drop should be considered to be due to and temporally related to the bleeding event.

the criteria for a major bleed but prompts a clinical response, in that it leads to at least one of the following:

- A hospital admission for bleeding
- or
- A physician guided medical or surgical treatment for bleeding
- or
- A physician guided change, interruption¹ or discontinuation of study drug.

Definition of a minor bleed

Minor bleeds are clinical bleeds that do not fulfil the criteria for major bleeds. Minor bleeds will be further divided to those that are CRNMBE, (see above) and those that are not.

Definition of a life-threatening bleed

Major bleeds are to be classified as life-threatening if they meet one or more of the following criteria:

- Fatal, or symptomatic intracranial bleed; reduction in haemoglobin of at least 5g/dL; transfusion of at least four units of blood or packed cells, associated with hypotension requiring the use of i.v. inotropic agents; necessitated surgical intervention.

Definition of intracranial haemorrhage (ICH)

Intracranial haemorrhage (ICH) comprises the subtypes of intracerebral bleeds, subdural bleeds, epidural bleeds and subarachnoid bleeds and will be recorded.

Definition of a fatal bleeding

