6.2.2 Treatment period(s)

All tests for the visits in the treatment phase are detailed in the Flow Chart.

After eligibility has been confirmed and all Visit 1 procedures done, Visit 2 can be conducted including randomisation via IRT. Screening and randomisation can be on the same day, depending on the availability of the screening laboratory results.

Randomisation can occur immediately after successful screening and up to 120 hours post PCI, however, randomisation within 72 hours is preferable. The first dose of trial medication

Proprietary confidential information.

© 2016 Boehringer Ingelheim International GmbH or one or more of its affiliated companies. All rights reserved.

This document may not - in full or in part - be passed on, reproduced, published or otherwise used without prior written permission.

will be taken between 6 hours after sheath removal and preferably within 72 hours post PCI (end of intervention i.e. when the last catheter used for PCI is removed), with haemostasis assured, however randomisation up to 120 hours post PCI is allowed.

Treatment visits will take place approximately every three months for the first 12 months of treatment and every six months thereafter. After month 12, phone calls will be conducted in between regular clinic visits. These calls are designed to encourage accurate and timely event reporting and continued engagement of patients.

As this is an OE driven trial, patients will remain in the treatment period until the necessary number of OEs is reached. Permanent study drug discontinuation is only justified when clear, persistent contraindications arise or when the patient requests to be withdrawn from study drug, see [Section 3.3.4.1](#).

All patients who discontinue treatment must be followed up until the end of the study. Patients who discontinue treatment must continue to be followed up according to the visit schedule until the end of the study. At these visits (as indicated in the [Flow Chart](#)) ECGs will be performed and the collection of AEs, OEs (including completion of the bleeding questionnaire) and use of concomitant medication will be made.

Patients that are not actively taking study drug may be less motivated to adhere to the study visit schedule. Investigator and site staff should work to detect early signs of losing interest and readily present such patients (not actively taking study drug) with the following opportunities to encourage continued participation:

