7.2 NULL AND ALTERNATIVE HYPOTHESES

Two safety hypotheses (110mg Dabigatran Etexilate (DE-DAT) vs. warfarin-TAT and 150mg DE-DAT vs. warfarin-TAT) will be tested:

1. 110mg DE-DAT is non-inferior to warfarin-TAT with respect to MBE/CRNMBE over the duration of the trial
2. 150mg DE-DAT is non-inferior to warfarin-TAT with respect to MBE/CRNMBE over the duration of the trial.

To control the Type I error rate at a one-sided 0.025 level, a hierarchical procedure for multiple testing will be used to test the above hypotheses. Additional testing for safety and efficacy endpoints will also be included in this hierarchical procedure. The following hierarchical procedure will be applied:

Step 1 – Non-inferiority of 110mg DE-DAT to warfarin-TAT in MBE/CRNMBE is met at the one-sided 0.025 level of significance

Step 2 – Non-inferiority of 150mg DE-DAT to warfarin-TAT in MBE/CRNMBE is met at the one-sided 0.025 level of significance

Step 3 – Non inferiority of 150mg DE-DAT and 110mg DE-DAT combined to warfarin-TAT in DTE and unplanned revascularisation by PCI/CABG is met at the one-sided 0.025 level of significance

Proprietary confidential information.

© 2016 Boehringer Ingelheim International GmbH or one or more of its affiliated companies. All rights reserved.

This document may not - in full or in part - be passed on, reproduced, published or otherwise used without prior written permission.

Step 4 – Superiority of 110mg DE-DAT to warfarin-TAT in MBE/CRNMBE is met at the one-sided 0.025 level of significance

Step 5 – Non inferiority of 150mg DE-DAT and 110mg DE-DAT combined to warfarin-TAT in DTE is met at the one-sided 0.025 level of significance

Step 6 – Superiority of 150mg DE-DAT to warfarin-TAT in MBE/CRNMBE is met at the one-sided 0.025 level of significance

If any of the steps above fail to meet statistical significance, the testing procedure will stop at that step and subsequent tests will not be performed.

The Non-Inferiority (NI) margin used for MBE/CRNMBE will be 1.38 (on the relative HR scale). See [Section 7.6](#) for a clinical justification of this margin. The upper bound of the Wald confidence interval (CI) of the HR of DE-DAT vs. warfarin-TAT (one-sided 97.5%) will be compared to this NI margin for the NI testing.

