7.6 DETERMINATION OF SAMPLE SIZE

This is an event-driven trial where it is assumed that the first patient recruited into the study will be followed up for a maximum of approximately 30 months and the last patient recruited into the trial will be followed up for a minimum of 6 months. It is assumed that patient accrual will be approximately uniform over the 24 month recruiting period.

The proportion of patients with at least one MBE/CRNMBE at one year is estimated to be 14% based on current blinded trial data.

A relative NI margin for the original co-primary endpoint (DTE) was chosen in analogy to recent SPAF trials with primary endpoints of stroke/SE, where 1.38 was used by the FDA for ximelagatran, apixaban, rivaroxaban and dabigatran to preserve at least 50% of the relative reduction (on the log scale) in the risk associated with warfarin in six previous (historical), randomised, controlled trials. See publication by Jackson K, Gersh BJ, Stockbridge N, et al. [[R08-2662](#)]. The same NI margin has been applied to MBE/CRNMBE as it was considered the most clinically relevant available reference in the absence of any other type of data.

The overall sample size is driven by the non-inferiority comparison of MBE/CRNMBE between 110mg DE-DAT or 150mg DE-DAT and warfarin-TAT. With $\alpha=0.025$ (one-sided) and 14% of patients with at least one event at one year, 334 patients with at least one MBE/CRNMBE in each pair of treatment groups (i.e. 167 patients with MBE/CRNMBE per treatment group) are required to achieve 83.6% power for this endpoint, yielding a final sample size estimated at 834 patients in each treatment group (i.e. 2502 randomised patients in total). Therefore approximately 500 patients with at least one MBE/CRNMBE are required in total across the three treatment groups.

Proprietary confidential information.

© 2016 Boehringer Ingelheim International GmbH or one or more of its affiliated companies. All rights reserved.

This document may not - in full or in part - be passed on, reproduced, published or otherwise used without prior written permission.

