7.4 PRIMARY ENDPOINT

This is a prospective, randomised, open label, blinded endpoint (PROBE), active comparator trial and the clinical endpoints are being adjudicated by an IAC in a blinded fashion. The IAC

Charter contains details of the outcome event adjudication criteria. The study will employ a time to first event analysis (using a stratified Cox proportional hazards regression model) and it is assumed that all patients will be observed until first primary endpoint event or until the last patient entered has completed at least six months of treatment (up to an anticipated maximum duration of approximately 30 months for the first patient entered). The trial will be monitored by an independent DMC.

This study is designed to test two safety hypotheses in NVAf patients that have undergone a successful PCI (elective or due to ACS) with stenting and were treatment naïve or were receiving oral anticoagulant treatment (either with warfarin, another VKA or other novel oral anticoagulant) before the procedure.

The primary endpoint, measured from date of randomisation to end of observation period, is:

- Time to first ISTH MBE or CRNMBE

as determined by the IAC. Only positively adjudicated events will be included in the analyses. They will be analysed using the stratified Cox proportional hazards regression model including age group (non-elderly or elderly [<70 or ≥ 70 years old in Japan and <80 or ≥ 80 years old everywhere else]) as a stratifying factor and treatment arm (110mg DE-DAT vs warfarin-TAT and 150mg DE-DAT and 110mg DE-DAT combined vs warfarin-TAT). For the 150mg DE-DAT versus warfarin-TAT comparison, an unstratified model will be applied comparing 150mg DE-DAT versus warfarin-TAT (excluding elderly EU/ROW patients in the warfarin-TAT group). In addition, an unstratified sensitivity analysis of the non-elderly patients only will be conducted.

Models will be fitted for each comparison separately (110mg DE-DAT vs warfarin-TAT and 150mg DE-DAT vs warfarin-TAT). The Breslow method [9] will be used to handle tied failure times.

The primary analysis will be performed under the intention-to-treat framework on the FAS. Patients who discontinue study medication will be followed until the end of the trial for vital status, ECGs, AEs, OEs (including completion of the bleeding questionnaire) and concomitant medications. All patients will be analysed according to the treatment arm to which they were randomised.

Survival time

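### The third CRNMBE criterion cannot be met after study drug is permanently stopped, and the documents conflict on haematology off drug, although off-drug time counts in the primary analysis

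*Protocol*

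**What the plan says.** **Off-drug time counts.** Protocol 7.3.1 analyses all randomised patients as randomised and follows those who stop treatment to the end of the trial. SAP 7.4 censors patients who stopped early at their final visit, not at their last dose. Protocol Appendix 10.2 expects that most will still need an anticoagulant.

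**The endpoint definition.** Protocol 5.2.2.1 gives three alternative routes to a CRNMBE: hospital admission for the bleed, physician-guided treatment of it, or a physician-guided change, interruption "or discontinuation of study drug". A footnote counts an interruption only if more than one dose is omitted because of the bleed.

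**Assessments after stopping.** Flow Chart footnote 6 says "Patients who discontinue study treatment early should continue to attend regularly scheduled visits". For such attendances Protocol 6.2.2, which also points to the Flow Chart, specifies the following: "ECGs will be performed and the collection of AEs, OEs (including completion of the bleeding questionnaire) and use of concomitant medication will be made". SAP 7.4 has such patients "followed until the end of the trial for vital status, ECGs, AEs, OEs (including completion of the bleeding questionnaire) and concomitant medications". Neither list names haematology. Protocol 3.1, however, has haematology taken at every clinic visit. The Flow Chart marks it at the scheduled clinic visits and at end of treatment, does not separate on-drug from off-drug patients, and shows none at Visit 990, the final visit for patients who stopped early.

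**The safeguard.** Among its measures against reporting bias in an open-label trial, Protocol 3.2 states: "Any decrease in haemoglobin of >2g/dL will be similarly investigated".

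**The concern.** The same bleed with the same clinical response can be an event on drug and a non-event off drug. On study drug, a physician who responds to an overt bleed by withholding the anticoagulant for more than one dose creates a CRNMBE. Off study drug, a physician who withholds the replacement anticoagulant does not, unless admission or treatment also occurs. Blinded adjudication cannot repair this, because the asymmetry lies in the definition being applied.

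The second part concerns detection. If a site takes the lists in 6.2.2 and SAP 7.4 as complete, it draws no haemoglobin off drug, and the Section 3.2 query has no scheduled samples to work from in those patients.

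Both parts lower the completeness of the primary endpoint off drug relative to on drug. With equal stopping in the arms this costs events. With unequal stopping it shifts the hazard ratio in the two non-inferiority tests (Steps 1 and 2) and the two superiority tests (Steps 4 and 6) on MBE/CRNMBE.

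**Working it through.** **Inputs from the documents.** One-sided alpha 0.025 and margin 1.38 (Protocol 7.2). From Protocol 7.6: "334 patients with at least one MBE/CRNMBE in each pair of treatment groups", power 83.6%, 14% with an event at one year, uniform accrual over 24 months, follow-up of 6 to about 30 months, 834 patients per arm.

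**1. The plan's own figures.** Assume a true hazard ratio of 1, which the protocol does not state.
- Standard error of log HR = √(4/334) = 0.1094, and ln 1.38 = 0.3221.
- Power = Φ(0.3221/0.1094 − 1.960) = Φ(0.983) = 83.7%, against 83.6% stated.
- Event hazard λ = −ln 0.86 = 0.1508 per year.
- P(event) = 1 − (e^(−0.5λ) − e^(−2.5λ))/(2λ) = 0.1994.
- 167/0.1994 = 838 per arm, against 834 stated.

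The planning figures reproduce, and this point does not change them.

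**2. Off-drug share of at-risk time (assumed stopping).** Let a proportion p stop by one year at a constant hazard δ = −ln(1 − p), independent of bleeding. Write G(t) for the probability that planned follow-up exceeds t. The share is f = ∫G(t)e^(−λt)(1 − e^(−δt))dt / ∫G(t)e^(−λt)dt. For p = 15%, f = 0.120. For p = 25%, f = 0.198.

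**3. Effect on the hazard ratio (assumed ascertainment).** Let u be the proportion of off-drug events that go uncounted. To a close approximation the true HR is multiplied by m = (1 − f_D·u)/(1 − f_W·u), with D for a dabigatran arm and W for warfarin. For 25% stopping on dabigatran and 15% on warfarin:
- u = 10%: 0.9802/0.9880 = 0.992.
- u = 40%: 0.9208/0.9520 = 0.967. Exact integration, which keeps patients with an uncounted event at risk, gives 0.966.

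**4. Both directions, by exact integration over u = 10% to 40%.** The error column uses Φ(−ln m/0.1094 − 1.960) at a true HR of 1.38. The power column uses Φ((ln 1.38 − ln m)/0.1094 − 1.960) at a true HR of 1.

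| Stopped by year 1 (dabigatran vs warfarin) | HR multiplied by | One-sided error (nominal 2.5%) | Power (83.7% without bias) |
|---|---|---|---|
| Equal | 1.000 | 2.5% | 83.7% at 334 events |
| 25% vs 15% | 0.992 to 0.966 | 3.0% to 5.0% | 85.5% to 90.3% |
| 15% vs 25% | 1.008 to 1.035 | 2.1% to 1.2% | 81.9% to 74.9% |
| 30% vs 10% | 0.984 to 0.934 | 3.5% to 9.1% | 87.1% to 94.6% |

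Events lost per 834-patient arm are about 2 to 8 at 15% stopping and 3 to 12 at 25%, out of about 166. The stopping rates and u are assumptions. The documents state neither.

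**The case against.** - **A reader might infer that haematology ends when drug is stopped.** No sentence says so. Section 3.1 points the other way, the 6.2.2 list is not worded as exclusive, and its pointer to the Flow Chart can be read as letting the Flow Chart govern. The rationale in Amendment 1 says the pointer was added to guide which tests apply off drug, which does not settle the reading. What stands is a conflict between passages.
- **A scheduled haemoglobin does not make an event.** Section 5.2.2.1 requires overt bleeding with a related fall. The bleeding questionnaire and outcome-event reporting continue off drug, and a local haemoglobin can still support a major bleed. This is right, and it limits the haematology part to bleeds that would otherwise go unreported.
- **The definitional gap is narrow.** Admission and physician-guided treatment still qualify, the wording is the same in every arm, and on drug a single omitted dose does not qualify either. The adjudication charter, which is not among the documents, might address it. The protocol definition as written still leaves the gap open.
- **A reader might infer that the bias favours dabigatran.** The documents do not support a direction. The rationale in Amendment 2 records patients previously on novel anticoagulants who were unwilling to be randomised to warfarin, so more stopping on warfarin is at least as plausible. That would work against dabigatran.
- **The model overstates off-drug time to some extent.** A patient whose study drug is stopped by the physician for an overt bleed has already had the event.
- **On-treatment analyses are planned** (Protocol 7.3.1, SAP 7.4). They avoid most off-drug time, and comparison with the primary result is informative. They answer a different question, however, and cannot separate selection from incomplete measurement. No planned analysis in the text provided removes the study-drug criterion.

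**Conclusion.** The definitional part is firm: after permanent discontinuation the third CRNMBE criterion cannot be met, while the primary analysis keeps the patient at risk. The haematology part is a conflict to reconcile. Sections 6.2.2 and SAP 7.4 omit it, Section 3.1 includes it, and the Flow Chart shows none at Visit 990, so the haemoglobin safeguard may or may not cover these patients.

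The likely effect is small. Under 15% versus 25% stopping, the hazard ratio moves by about 1–3%, toward dabigatran if dabigatran patients stop more and against it if warfarin patients stop more. The 30% versus 10% row in the table shows sensitivity to a large imbalance and has no basis in the documents as an expected value. Equal stopping and equal ascertainment give no bias. The point merits correction because it touches the primary endpoint of an open-label trial and costs little to close. It is not evidence that the primary result will be wrong.

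**What to change.** 1. In Protocol 5.2.2.1 and the adjudication charter, extend the third criterion to *study drug or, in a patient not currently taking study drug, the anticoagulant given in its place*.
2. In SAP 7.4, add a sensitivity analysis of the primary endpoint that drops the third criterion in all arms. The adjudication record must show which criterion qualified each event. Report off-drug follow-up by arm beside it, so that the reader can judge the scope for bias.
3. Reconcile Protocol 3.1 with 6.2.2, SAP 7.4 and the Flow Chart by stating that the haematology sample and the Section 3.2 haemoglobin query continue at clinic visits attended after discontinuation, including Visit 990.

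The cost is definition and charter wording, one extra analysis, and one haematology tube at visits the patient already attends. A few more events will need adjudication. Patients on telephone-only follow-up will still not be sampled. Items 1 and 3 help only follow-up that has not yet taken place, unless past bleeds are re-adjudicated. Item 2 needs no new data if the qualifying criterion is on record.
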